1. TRIAL SUMMARY

Title	Efficacy of Gabapentin in Treating Pain in Children with Severe Neurological Impairment
Brief title	Gabapentin Trial
Primary registry and trial number	2020GabTrial
Secondary identifying numbers	Clinical Trials.gov: NCT03464773 SCA-145104 RI MUHC Ref# 7733
Sources of monetary or material support	Canadian Institutes of Health Research (CIHR) SPOR Networks in Chronic Disease, CHILD-BRIGHT
Primary sponsor	[name]
Study officials/Investigators	[name], [name], [name], [name]
Central contact	[name]
Number of centers	1
Primary objective	Evaluate the effectiveness of gabapentin to decrease pain and irritability in children with SNI, when source of pain and irritability is attributed to neurological dysregulation and not to a nociceptive-inflammatory cause
Secondary objective	 Identify the optimal dosing of gabapentin in reducing pain and irritability Identify the latency time for gabapentin to show effectiveness Evaluate the safety and tolerability of gabapentin
Exploratory objective	Evaluate whether parent/caregiver stress and function improve if gabapentin reduces child's pain and irritability
Interventions	Participants will receive liquid gabapentin, compounded from Teva-Gabapentin (gabapentin) 400 mg capsules (DIN 02244515). cf. below

Key eligibility criteria	Children 3 to 18 years old with severe neurological impairment who are experiencing pain and/or irritability of unknown origin (PIUO)
Study design	Repeat measures single cross-over trial (treatment and placebo)
Randomization	Computer-generated, simple randomization (starting with treatment or placebo). Each participant serves as their own control.
Target sample size	10
Study duration	Total study duration 12 months, participant study duration 4 months
Medication administration and dosing	Gabapentin capsules will be compounded with flavourings to create a 100 mg/mL oral solution. The starting dose will be 5 mg/kg/day as oral liquid or via g-, j-tube. The dose will be escalated as described in Section 6.2. The maximum dose is 60 mg/kg/day in participants < 15 kg, or 45 mg/kg/day (675 mg) in participants > 15 kg.
Primary outcomes	The pain and irritability score on the NCCPC-R through days 11-19 on active drug compared to placebo. An 11-point decrement in the NCCPC-R score with no rebound x 3 days is considered clinically meaningful minimum change (improvement)

Secondary outcomes	 For patients who benefited from gabapentin, identification of the lowest dose that was effective in reducing pain scores, as shown by a 50% reduction in the NCCPC-R score compared to baseline during days 11-19 on active drug For patients who benefited from gabapentin, identification of the maximal effect dosage as measured by the largest improvement in the NCPCC-R score compared to baseline during days 11-19 on active drug. Identification of the latency time in days to the onset of maximum relief of pain and irritability as measured by the NCCPC-R score over days 0-19. Adverse Events Collection demonstrates the AE on treatment arm do not exceed the frequency found in 	
	gabapentin. PROMIS-57 scores on the treatment arm compared to the	
Exploratory outcomes	placebo arm.	
Outcome measures	Primary: NCPCC-R Secondary: NCPCC-R, Adverse Events Collection Exploratory: PROMIS-57	

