2.3. Trial Design

With the small sample size and time needed to titrate up to an effective dose, this trial proposes to use a single randomized multiple-measures cross-over design (N-of-1), with results aggregated over several subjects. This design is well-suited to outcomes that are highly specific to each individual and not amenable to precise measurement across a large cohort. The heterogenous nature

of pain and irritability responses in children are more likely to be personally specific and characteristic, rather than generalizable. The behavioural pattern is reflected in the structure of the standard tools for pain assessment in SNI that rely upon a catalogue of behaviour patterns that differ from one child to the next.^{3,29,50-52}

The proposed cross-over trial will use randomization and blinding of subjects and observers with placebo controls to reduce unexpected bias. A critical distinction is that each subject will serve as their own control and experiment, allowing for a finer assessment of the treatment efficacy within each patient.

In this trial, each patient will switch between gabapentin (G) and placebo (P). The sequence of whether G precedes P (GP) or P precedes G (PG) will be randomized by the study pharmacist, and neither the clinician nor the subject (parent/caregiver) will know the sequence.

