3.6. Sample size

We will enroll 10 participants in the gabapentin trial. In personalized trials, sample size refers to the number of assessments for each patient. As we had no prior data from which to estimate within patient day-to-day variability in pain scores nor an expected effect size for symptom reduction when comparing gabapentin to placebo in this population, we did not calculate statistical power a priori for the number of assessments per treatment period. Rather, the sample size for each personalized trial was based on collecting the maximal amount of data expected to be tolerable from the perspective of patient study burden. Ten participants is a sampling number based on current recruitment into the PIUO Study (REB #H16-03288) from which we expect to draw the majority of participants for this trial. This number, with the repeated measures obtained throughout the treatment periods should provide sufficient data to address the study goals.

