Randomization will be undertaken by the study pharmacist, using a computer-generated randomization. Before the 2 periods (pair of active drug (G) or placebo (P)) the pharmacist will generate a random code indicating whether G or P is to be given first. The randomization table will be kept in the Research Pharmacy office, which has restricted access. In case of a serious adverse event and when necessary, the randomization of any one participant can be unmasked to the Principal Investigator. This will be done through direct contact between the pharmacist and the Principal Investigator.

Study Contacts

Contact with study participants during the trial will consist of online surveys and telephone check ins. Contacts will be scheduled to overlap with changes in dose. Each contact will last approximately 10 minutes. The following study tools will be used at study contacts (see table 4 for a schedule of assessments at the time of study contacts):

- Health Update (Appendix 6) (midway through each sequence and at study end)
- Pain Survey (Appendix) (only on the first or last day of each block, not both)
- NCCPC-R (Appendix 7)
- PROMIS-57 (Appendix 8)
- Adverse Events Log (Appendix 10)
- Concomitant Medications (Appendix 11)

When the participant begins Sequence 2, the drug will be dispensed again in person.

Follow up

Two weeks past Study End the randomization sequence for individual participants will be unblinded and shared with the participants along with their individual results. The results will be presented numerically and graphically. Graphs showing the outcomes over time on the medication and placebo arms, summarizing the dosage used at individual outcome points will be provided. This will allow participants to make decisions regarding continuing gabapentin (in consultation with their primary caregiver) and is in keeping the Strategies for Patient Oriented Research (SPOR) principles that this clinical care trial is based on. At this time, the participant's caregiver will also be given the opportunity to provide feedback to the research team via the Participation Questionnaire (Appendix 9).

For any participant that experiences a SAE, there will be an initial contact at the time of the event and appropriate evaluation undertaken by the physician investigator. Another safety follow-up visit will be scheduled within 7 days following the final study visit to review the event. Additional follow-up may be done based on the investigator's medical judgment.

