Missed visits

If a participant misses a scheduled study visit or contact with prior permission, the researchers will try to contact him/her and schedule a visit as soon as possible. Participants who stop taking the study medication for any reason will be asked to complete the Final Study Visit.

Withdrawal from trial

A participant may be withdrawn from the trial due to the following reasons including, but not limited to:

- Participant's request
- Severe Adverse Events (SAE) and/or other safety reasons
- A new health condition appears that is suspected to require care or medications prohibited by the protocol

• It is in the participant's best interest according to the Investigator's clinical judgment

Participants are free to withdraw from the study at any time and for whatever reason, specified or unspecified, and without prejudice to his or her medical care by a physician.

All premature discontinuations and their causes must be documented by the Investigator on the appropriate CRF pages. The reason for, and date of, the discontinuation, and the date of the last dose of the study medication, must be recorded in the appropriate section of the CRF. While the treatment with the investigational product will discontinue if a participant withdraws from the trial, participants not completing the entire study should be fully evaluated (i.e., last study contact and follow up procedures performed), wherever possible.

Withdrawn participants will be replaced via ongoing recruitment in order to meet the goal of obtaining data from 10 participants completing the trial.

Early termination visit

If a participant withdraws or is removed from the trial for any reason prior to the completion of the trial, the reason for, and date of, the discontinuation, and date of the last dose of study drug, must be recorded in the appropriate section of the Case Report Form (CRF).

At the time of discontinuation, every effort should be made to ensure that: (1) Procedures and evaluations scheduled for the End of Study are performed, including the assessment of AEs. (2) Study drugs are returned and inventoried. (3) Study staff make an appointment for a safety follow-up visit if required.

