3.10. Statistical Methods

All data will be entered into a REDCap database, either directly from participants using a web-based entry system, or for those using paper, transferred from data collection sheets by a research assistant. The study cohort will be described in tables with descriptive statistics (mean, median and standard deviation) where appropriate. The primary method of analyzing the data was by systematic visual graphing of the pain scale over the exposure/placebo conditions. This is the method recommended by the CONSORT collaboration, extension for N-of-1 studies (CENT).⁵⁸

Data analysis for the primary outcome will be conducted within each N-of-1 trial and will also be aggregated across trials using measurements taken on days 11-19.

For each individual, the pain and irritability score on the NCCPC-R will be calculated over days 11-19 for both the treatment and control periods. These means will then be compared statistically using a Bayesian model, reporting the posterior mean difference using a non-informative prior for the means and variance. The posterior probability that the mean of the treatment is greater than the mean of the control will also be reported. Because of the use of non-informative priors, this analysis is very similar to a t-test.

We will also aggregate the means across participants using Bayesian linear mixed models in order to compare the average effect of the treatment as well as obtain better estimates of each individual's effect through borrowing of strength from others' data.

Additional analyses

Secondary outcomes will be assessed as follows:

- For each patient who benefits from gabapentin, the lowest dose that was effective in reducing pain scores will be calculated as the lowest dose that gives at least an 11 point reduction with no rebound over 3 days in the NCCPC-R score compared to baseline during day 11-19 on active drug. The set of lowest doses will be summarized descriptively.
- For each patient who benefits from gabapentin, the maximal effect dose will be calculated as the dose that gives the largest improvement in the NCPCC-R score compared to baseline during days 11-19 on active drug. The set of lowest doses will be summarized descriptively.

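### Simple randomization of treatment order in 10 children gives a 7:3 or worse split with probability 34%, which costs the group-level estimate precision or, if period is not modelled, exposes it to period shifts

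*Protocol*

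**What the plan says.** The protocol is consistent on how order is assigned. The Trial Summary gives "Computer-generated, simple randomization (starting with treatment or placebo"). Section 2.3 says that "The sequence of whether G precedes P (GP) or P precedes G (PG) will be randomized by the study pharmacist", and section 3.8 (Randomization) adds that before a child's two periods "the pharmacist will generate a random code indicating whether G or P is to be given first". No block, stratum or other balancing rule appears.

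The sample is small: "We will enroll 10 participants in the gabapentin trial" (section 3.6). Section 3.8 (Withdrawal from trial) states: "Withdrawn participants will be replaced via ongoing recruitment in order to meet the goal of obtaining data from 10 participants completing the trial". It does not say which sequence a replacement receives.

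Section 3.10 has two layers of analysis. Each child's day 11-19 means are compared, and of this comparison the protocol says: "Because of the use of non-informative priors, this analysis is very similar to a t-test". For the group: "We will also aggregate the means across participants using Bayesian linear mixed models in order to compare the average effect of the treatment". No period or sequence effect is named for the group model.

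**The concern.** Each child has one gabapentin period and one placebo period. Within a child, treatment and period therefore cannot be separated. At group level they can be, but only by setting children who took gabapentin first against those who took it second. Simple randomization does not protect the balance between these two groups when there are only 10 children.

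A shift between periods is plausible from the protocol's own text. Entry requires a Pain Survey score of C, D or E (section 3.2), so some regression to the mean may follow. Children already on gabapentin may be weaned before randomization (section 3.3). Section 3.8 expects caregiver beliefs to influence scores, and beliefs may change over the trial.

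At stake is the aggregate estimate, which section 2.2 makes part of the primary objective and section 2.1 expects to inform a larger trial.

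**Working it through.** **Inputs.** n = 10 (section 3.6); two sequences, gabapentin first (GP) or placebo first (PG) (section 2.3); simple randomization (Trial Summary); 11 points as the meaningful change (section 3.4). Two inputs are assumptions: an allocation probability of 0.5, since no ratio is stated, and the size of the period shift, for which the protocol gives no figure. The protocol offers no split probability or power figure to reproduce.

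**Step 1: chance of imbalance.** The number of GP children is binomial(10, 0.5).

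- Exactly 5:5: 252/1024 = 24.6%
- 5:5 or 6:4: (252 + 420)/1024 = 65.6%
- 7:3 or worse: 2 × (1 + 10 + 45 + 120)/1024 = 352/1024 = 34.4%
- 8:2 or worse: 2 × (1 + 10 + 45)/1024 = 112/1024 = 10.9%
- 9:1 or worse: 2 × (1 + 10)/1024 = 22/1024 = 2.1%

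**Step 2: no period term.** Let τ be the treatment effect (gabapentin minus placebo) and π the common shift from period 1 to period 2. A PG child's difference has expectation τ + π, and a GP child's τ − π. The unadjusted group mean then has expectation τ + π(nPG − nGP)/10, so the absorbed share of π is |nPG − nGP|/10.

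**Step 3: with a period term.** The estimate is the average of the two sequence means, and the shift cancels. Variance relative to 5:5 is (1/nGP + 1/nPG)/(1/5 + 1/5).

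| Split | Share of shift absorbed (no period term) | Bias in points for π = 2 / 5 / 10 (assumed) | Relative variance (period term) |
|---|---|---|---|
| 5:5 | 0 | 0 / 0 / 0 | 1.00 |
| 6:4 | 0.2 | 0.4 / 1.0 / 2.0 | 1.04 |
| 7:3 | 0.4 | 0.8 / 2.0 / 4.0 | 1.19 |
| 8:2 | 0.6 | 1.2 / 3.0 / 6.0 | 1.56 |

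The direction of the bias depends on which sequence is in excess. If scores fall over time, an excess of PG children flatters gabapentin and an excess of GP children counts against it.

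**Step 4: averages over draws.** The mean absolute share absorbed is (420 × 0.2 + 240 × 0.4 + 90 × 0.6 + 20 × 0.8 + 2 × 1.0)/1024 = 252/1024 = 24.6%. The signed share averages zero. The mean relative variance with a period term, leaving out 10:0 (probability 0.2%, where the adjusted estimate does not exist) and using 2.78 at 9:1, is (252 × 1 + 420 × 1.042 + 240 × 1.190 + 90 × 1.563 + 20 × 2.778)/1022 ≈ 1.15.

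**Step 5: simulation check.** With τ = 0, π = 5 and an assumed standard deviation of 10 for the within-child difference, the mean unadjusted estimate was 2.01 at 7:3 and 3.00 at 8:2. The period-adjusted estimate averaged about 0 in both cases. Its standard deviation was 3.46 against 3.17 unadjusted at 7:3, and 3.95 against 3.16 at 8:2, in line with step 3.

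**The case against.** Simple randomization is a legitimate method. Averaged over all possible draws, even the unadjusted estimate is unbiased; the leak exists only conditionally on an uneven split. It also needs a group model without period, and the choice of fixed effects is commonly left to the statistical analysis plan, which is not at hand. The protocol's silence on a period term is therefore not itself an error. All of this stands. What a later analysis plan cannot do is restore balance once the children have been allocated, so the precision cost would remain.

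The case for a large shift is also limited. Entry does not depend on an NCCPC-R threshold. Some children arrive after a 2-4 week pathway evaluation, and the windows compared are days 11-19 of each period, so part of any regression to the mean may be over before the first window. This too stands, and is why the shift is shown as a range. A reader might infer that a bias of 4 to 6 points is expected; the protocol supports no such value. Likewise, the near-tripling of variance at 9:1 belongs to a case with about 2% probability once 10:0 is included.

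Finally, section 3.10 makes visual graphing the primary method and analyses each child separately. Balancing sequences does nothing for those within-child comparisons, in which "Each participant serves as their own control", nor does it remove unequal carryover.

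Simple randomization has one real advantage here: every code stays unpredictable although families are unblinded two weeks after their study end. Any restricted scheme gives up some of that, and the fix must respect it.

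**Conclusion.** The point holds for the aggregate estimate only. Simple randomization of 10 children carries a 34% chance of a 7:3 or worse split and an 11% chance of 8:2 or worse, assuming equal allocation odds. The consequence is one of two things. Without a period term, 40% or 60% of any common shift enters the estimate, given the split. With one, there is no such bias, but variance rises 4% at 6:4, 19% at 7:3 and 56% at 8:2, about 15% on average. In two thirds of draws (65.6%) the rise is 4% or less.

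A reader might conclude that the planned randomization makes the trial's result biased. The documents do not support that: the procedure is unbiased over draws, the shift size is unknown, and the final model may include period. What they do support is that the stated method gives up balance, and with it precision, that could be secured at little cost in a sample set by recruitment and not by a power calculation.

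**What to change.** 1. In the Trial Summary and section 3.8 (Randomization), replace simple randomization with a permuted-block list held by the pharmacist, using small block sizes that vary at random and are not disclosed, for example 2 and 4. Complete blocks are balanced, and a part-filled block of 4 can leave an excess of at most 2, so 10 allocations end at 5:5 or 6:4. Do not promise exactly 5:5: with a known total of 10 and each child unblinded two weeks after study end, the last codes could be deduced.
2. In section 3.8 (Withdrawal from trial), give each replacement the next unused code on the list. Reusing the withdrawn child's sequence would be unsafe: a serious adverse event can lead to both withdrawal and unmasking to the Principal Investigator, so the replacement's order could be known before enrolment.
3. In section 3.10, include period as a fixed effect in the aggregate mixed model. It is needed in any case, because withdrawals may leave the completers somewhat unbalanced.

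The cost is a new list before the first child is randomized, two short text changes and one model term. The downside is that some codes become more guessable as children are unblinded; varying, undisclosed block sizes reduce this but do not abolish it.

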Summary: This study uses a rapid and safe dose escalation to the widely accepted therapeutic range where evaluation of response will be undertaken with frequent scoring. Different maximal doses are used for children < or ≥ 15 kg, based on pharmacokinetic data. Doses are titrated to clinical effect or maximum target dose, whichever is lower. Once in the therapeutic range, doses change after 3 days if there is not an adequate reduction in symptoms. For any subject that obtains clinical benefit below maximal dose, then they will be held at that dose for the remainder of that period until such time as the scheduled wean begins. At the end of each treatment period there is a wash-out.

Starting Dose: The starting dose of gabapentin will be 5 mg/kg administered as oral liquid or via gastric or jejunal routes. On Day 1 of the study, the gabapentin will be administered once at bed-time and then increased according to the schedule shown in Table 1.

Dose Escalation: The dose will be increased every 3^{rd} - 4^{th} day in a step wise fashion of 13% - 50%, starting with the evening dose in order to accommodate sedation. The maximum dose for subjects will be as follows: < 15 kg to 60 mg/kg day and \geq 15 kg to 45 mg/kg/day. Dose titration will be to a maximum target dose (based on weight as described, < 15 kg, > 15kg) or to clinical effect, whichever is lower. The dose escalation scheme is based upon expert consensus and personal communication with [name], [name], and upon review with the BC Children's Hospital research pharmacist. \cdot , 56.

Some children with PIUO and SNI have been given gabapentin empirically by their health care provider, often without any subsequent, detailed assessment of benefit. Many times, the medication is continued because of its low side-effect profile and overall safety compared with other analgesics. If a subject is currently on gabapentin at the time of enrolment, and the parent/caregiver wants an evaluation of its effectiveness, then the subject can be enrolled in this study with the following approach:

After appropriate enrolment and consent, the subject will be weaned off of gabapentin, in a stepwise manner with 25% reductions in dose every 3rd day. Once they are no longer on the active drug, they will be randomized to active drug or placebo like all other study participants.

Gabapentin Risks and Precautions

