The risk of serious side effects of respiratory depression with concomitant use with opioids is acknowledged (BC Children's Hospital Integrated Pain Service Gabapentin Information http://www.bcchildrens.ca/Pain-Services-Site/Docu-Sheet. Accessed at: ments/BCCH1455Gabapentin.pdf. Retrieved on October 4, 2020). A minority of patients might be on opioids. Dose adjustments will be added when gabapentin is used with a concomitant opioid or other CNS depressant medication: the family will be advised to return to the previous stable, safe dose in the protocol, and the subject will remain at that dose with no further escalation for the duration of the trial arm. This schedule will be duplicated on the parallel arm (active drug or placebo) to maintain masking. The participants are highly monitored, often with continuous oxygen saturation monitoring and/or "baby-cam" devices observing them during sleep. During the daytime they are with family, or professional caregivers (aides, nurses, etc.). These individuals will be advised to watch for respiratory depression and sedation that occur well before fatal apnea, and how to respond.

While there are no prohibitions on concomitant care, any care or medications unrelated to the trial will be noted in the CRFs for each participant.

Participants are sometimes obtaining respite care at facilities with nursing and physician care. Medical reconciliation is done at each admission. Parents will be provided with a letter to share with these programs outlining the study, the drug being tested, and a 24-hour pager to contact for further information or concerns

Active Participants < 15kg in mg per kg

Day	Morning mg/kg	Noon mg/kg	Evening mg/kg	Total mg/kg per day	% Change
1*	0	0	5	5	0
2	0	5	5	10	100%
3	5	5	5	15	50%
4	5	5	5	15	0%
5	5	5	10	20	33%
6	5	5	10	20	0%
7	5	5	10	20	0%
8	10	10	10	30	50%
9	10	10	10	30	0%
10	10	10	10	30	0%
11	13.3	13.3	13.3	40	33%
12	13.3	13.3	13.3	40	0%
13	13.3	13.3	13.3	40	0%
14	17	17	17	50	25%
15	17	17	17	50	0%
16	17	17	17	50	0%
17	20	20	20	60	20%
18	20	20	20	60	0%
19	20	20	20	60	0%
20	13.3	13.3	13.3	40	-33%
21	6.7	6.7	6.7	20	-50%
22	0	5	5	10	-50%
23	0	0	5	5	-50%
24	0	0	0	0	-100%
25	0	0	0	0	0%
Switch over*	-	-	-	-	-

^{*}Day one or 26 if switching over, not both.

Active Participants > = 15kg in mg per day

Day	Morning mg	Noon mg	Evening mg	Total mg/kg per day	Total mg/day	% Change
1*	0	0	75	5	75	0
2	0	75	75	10	150	100%
3	75	75	75	15	225	50%
4	75	75	75	15	225	0%
5	100	100	100	20	300	33%

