6	100	100	100	20	300	0%
7	100	100	100	20	300	0%
8	150	150	150	30	450	50%
9	150	150	150	30	450	0%
10	150	150	150	30	450	0%
11	200	200	200	40	600	33%
12	200	200	200	40	600	0%
13	200	200	200	40	600	0%
14	225	225	225	45	675	13%
15	225	225	225	45	675	0%
16	225	225	225	45	675	0%
17	225	225	225	45	675	0%
18	150	150	150	30	450	-33%
19	150	150	150	30	450	0%
20	100	100	100	20	300	-33%
21	100	100	100	20	300	0%
22	50	50	50	10	150	-50%
23	25	25	25	5	75	-50%
24	0	0	0	0	0	-100%
25	0	0	0	0	0	0%
Switch over*	_	-	-	-	_	-

^{*}Day one or 26 if switching over, not both.

Inactive

Day	Morning mg/kg	Noon mg/kg	Evening mg/kg	Total mg/kg per day	% Change
1*	0	0	0	0	0%
2	0	0	0	0	0%
3	0	0	0	0	0%
4	0	0	0	0	0%
5	0	0	0	0	0%
6	0	0	0	0	0%
7	0	0	0	0	0%
8	0	0	0	0	0%
9	0	0	0	0	0%
10	0	0	0	0	0%
11	0	0	0	0	0%
12	0	0	0	0	0%
13	0	0	0	0	0%
14	0	0	0	0	0%
15	0	0	0	0	0%
16	0	0	0	0	0%
17	0	0	0	0	0%
18	0	0	0	0	0%
19	0	0	0	0	0%
20	0	0	0	0	0%
21	0	0	0	0	0%
22	0	0	0	0	0%
23	0	0	0	0	0%
24	0	0	0	0	0%
25	0	0	0	0	0%
Switch over*	0	0	0	0	0%

^{*}Day one or 26 if switching over, not both.

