6.2. Schedule of Enrolment, Interventions, and Assessments

Gabapentin Trial Diagrams and Summaries

Table 3 shows which assessments happen during specific phases of the trial. Table 4 shows the exact timepoint assessments are administer

Trial Design Summary

- Repeated Measures Single Cross-Over Trial (Treatment and Placebo)
- We will recruit 10 study participants. These participants will have completed the PIUO Pathway without resolution of pain. They will have severe neurological impairment and unexplained, untreated pain.
- The study participants will be randomized to treatment or placebo arms. This first session will take 25 days. During this time the treatment arm gabapentin dose will be slowly increased until an effective dose or maximum dose (60mg/kg/day) is reached, whichever comes first.
- The participants will then undergo a three-day long washout period, where neither drug nor placebo will be administered.
- Following this, the participants that were on placebo previously will switch to gabapentin treatment and those who were on gabapentin treatment will switch to placebo. This will again go on for 25 days, with the gabapentin dose increasing throughout.
- NCCPC-R, PROMIS-57 and Pain Surveys will be administered throughout the trial to obtain data
- The total participant time will be around 55 days.
- The diagram below depicts the Gabapentin trial design.

N-of-1 Design

The Gabapentin Trial will use an N-of-1 design. This means that each participant will be his or her own experiment, acting as both treatment and placebo participants. In an N-of-1 trial, each participant's treatment data is compared to his or her own placebo data, and the results are specific to

the individual participant. A small "N" such as 10 (as we are going to recruit for the Gabapentin Trial) can provide an adequate amount of data when using an N-of-1 design because 10 separate data sets and results will be produced. Multiple N-of-1 trials that are conducted on similar patients taking similar drugs can be amalgamated to give broader results.

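### For children above 15 kg the protocol gives two different gabapentin doses: the fixed-mg table matches the stated mg/kg doses only at exactly 15 kg

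*Protocol*

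**What the plan says.** Section 1 (Trial Summary) gives the upper limits: "The maximum dose is 60 mg/kg/day in participants < 15 kg, or 45 mg/kg/day (675 mg) in participants > 15 kg".

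The text of Section 3.3 (Interventions) doses by weight. It opens with "The starting dose of gabapentin will be 5 mg/kg administered as oral liquid or via gastric or jejunal routes". It sets the ceiling at 60 mg/kg/day below 15 kg and 45 mg/kg/day from 15 kg upward. On the end point of titration it says "Dose titration will be to a maximum target dose (based on weight as described, < 15 kg, > 15kg) or to clinical effect, whichever is" (the sentence ends by choosing the smaller of the two). It names no limit in mg. For the steps after Day 1 it refers to Table 1.

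The dosing tables in Section 3.3 use different units for the two bands. The first is headed "Active Participants < 15kg in mg per kg" and contains only mg/kg. The second is headed "Active Participants > = 15kg in mg per day". Its morning, noon and evening doses are in mg, and its daily totals appear in both mg/kg and mg. The Day 14 row reads "14 225 225 225 45 675 13", that is, three doses of 225 mg, labelled 45 mg/kg/day, totalling 675 mg/day, a 13% increase.

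Section 1 also says "The dose will be escalated as described in Section 6.2". The only ceiling in the text of Section 6.2 is "until an effective dose or maximum dose (60mg/kg/day) is reached, whichever comes first", with no weight condition attached.

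Section 3.2 admits children aged 3 to 18 years and sets no upper weight limit.

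**The concern.** A dose cannot be both a fixed number of mg and a fixed number of mg/kg across a whole weight band. One of the two statements must be wrong for every child above 15 kg, and the protocol does not say which. With eligibility running to age 18, this is not confined to the edge of the band.

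Three things depend on it.

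- **Primary outcome.** Section 3.3 aims to reach the accepted therapeutic range and assess response there. If the mg table is followed, a heavier child spends days 11-19 below the labelled mg/kg dose, and a null result could partly reflect that.
- **Dose-finding outcomes.** Secondary outcomes 2 and 3 report a dose as the result. If the mg table is followed and the printed mg/kg column is used to express the dose, the answer is too high above 15 kg. Families also receive individual results with the dosage used, to help them decide whether to continue gabapentin.
- **Safety.** Caregivers dose at home, and the protocol itself acknowledges respiratory depression when gabapentin is combined with opioids. A difference of two- to fourfold should not be left to interpretation.

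**Working it through.** **Inputs.** The table for 15 kg or more, days 1-23 (Section 3.3); the 45 mg/kg/day maximum (Sections 1 and 3.3); the 5 mg/kg start (Section 3.3); the 100 mg/mL solution (Sections 1 and 3.3). The protocol gives no weight distribution, so 20, 30 and 60 kg are assumptions.

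**1. Weight implied by the table.** Total mg/day ÷ labelled mg/kg/day:

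| Days | mg/day | Labelled mg/kg/day | Implied weight (kg) |
|---|---|---|---|
| 1 | 75 | 5 | 15.0 |
| 2 | 150 | 10 | 15.0 |
| 3-4 | 225 | 15 | 15.0 |
| 5-7 | 300 | 20 | 15.0 |
| 8-10 | 450 | 30 | 15.0 |
| 11-13 | 600 | 40 | 15.0 |
| 14-17 | 675 | 45 | 15.0 |
| 18-19 | 450 | 30 | 15.0 |
| 20-21 | 300 | 20 | 15.0 |
| 22 | 150 | 10 | 15.0 |
| 23 | 75 | 5 | 15.0 |

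All 23 non-zero rows imply exactly 15.0 kg, and the three doses add up to the daily total in each. The plan's own figure is reproduced, 45 × 15 = 675 mg, but only at that weight.

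**2. Labelled mean dose in the primary window, days 11-19, for a child who follows the full schedule.**

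- In mg: (3 × 600 + 4 × 675 + 2 × 450) ÷ 9 = 5400 ÷ 9 = 600 mg/day.
- As labelled: (3 × 40 + 4 × 45 + 2 × 30) ÷ 9 = 360 ÷ 9 = 40 mg/kg/day.

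**3. The two readings at weight W.**

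| | 20 kg | 30 kg | 60 kg |
|---|---|---|---|
| *If the mg table governs* | | | |
| Share of labelled dose, 15/W | 75% | 50% | 25% |
| Starting dose, 75/W (mg/kg; text says 5) | 3.75 | 2.5 | 1.25 |
| Maximum, 675/W (mg/kg/day; text says 45) | 33.75 | 22.5 | 11.25 |
| Mean over days 11-19, 600/W (mg/kg/day; labelled 40) | 30 | 20 | 10 |
| *If the mg/kg rule governs* | | | |
| Maximum, 45 × W (mg/day; table says 675) | 900 | 1350 | 2700 |
| Volume at 100 mg/mL (mL/day; 675 mg is 6.75) | 9.0 | 13.5 | 27.0 |
| *Ratio of the readings, W/15* | 1.33 | 2.0 | 4.0 |

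At 30 kg, the mean of 20 mg/kg/day over the primary window equals what the table labels as the dose for days 5-7.

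**4. Across the 15 kg boundary.** Under the fixed-mg reading a 14.9 kg child may reach 60 × 14.9 = 894 mg/day, while a 60 kg child stops at 675 mg/day.

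**The case against.** The strongest reply is that the protocol leans towards fixed mg. Section 3.3 sends the reader to Table 1 for every step after Day 1. In the table for heavier children the doses actually administered are in mg, the heading says mg per day, and Section 1 repeats 675 mg for the same group. On that view the defect is only a wrong mg/kg column and loose mg/kg wording. This makes the fixed-mg reading somewhat more likely but does not settle it. The same table prints mg/kg totals, and the Section 3.3 text sets a per-kg start (150 mg at 30 kg against the printed 75 mg) and a per-kg ceiling with no cap. No text gives precedence to either.

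The other replies carry limited weight.

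- The comparison is within each child against placebo, so a lower dose changes which dose is tested and does not bias the contrast. That is correct. The concern for the primary outcome is one of interpretation, and it arises only if the mg table is followed and the child does not respond at a lower step.
- The protocol does not say that the printed mg/kg column will be used for the dose-finding outcomes, and an analysis plan could fix the unit. That is also fair, so the harm to those outcomes is conditional.
- No Table 1 caption appears above the dosing tables in the text read here, so an explanatory note could have been lost. This is possible but unsupported; the footnotes under the tables are present and concern only the switch-over day.
- The missing weight condition in Section 6.2 and the pointer to that section are minor. The point does not depend on them.

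**Conclusion.** The concern holds. For every child above 15 kg, either the mg/kg figures or the mg figures are wrong, and the protocol does not say which. The two readings differ by W/15, which is 1.33, 2 and 4 times at 20, 30 and 60 kg. The arithmetic of the table is certain. The sizes rest on those assumed weights, and the days 11-19 means on a child who follows the full schedule. The pharmacy may have applied one rule consistently in practice, but the document does not state it. No overdose is asserted, and no view is taken on which rule is right. Because the intervention itself is undetermined for these children, this must be fixed before dosing.

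**What to change.** Amend Section 1, the Section 3.3 text and table, and Section 6.2 to a single rule. There are two options:

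- **(a)** Dose by mg/kg scaled to weight for all children, print the table for 15 kg or more in mg/kg, and state any absolute mg cap.
- **(b)** Use a fixed-mg schedule from 15 kg upward, and remove the mg/kg column and the mg/kg wording for that group.

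The choice is clinical and pharmaceutical. Relative to the printed mg table, option (a) raises the dose of a 60 kg child fourfold.

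In the same amendment, attach the below-15 kg condition to the 60 mg/kg/day in Section 6.2, and point Section 1 to the Section 3.3 tables. Use one form of the weight boundary throughout, since Section 1 leaves a child of exactly 15 kg in neither band.

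For secondary outcomes 2 and 3, report dose as mg actually given, from the daily tracker, divided by weight at the Baseline Visit. Section 3.8 lists weight among the vital signs at that visit. The footnote to Table 3 lets recent PIUO Study participants skip several baseline items, so the amendment should make clear that weight is measured in every child.

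The cost is one protocol amendment with ethics board approval, covering a few dosing statements and one table. If dosing has already finished, the reporting correction still applies.
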